## 1. STUDY OVERVIEW

---

**Background and rationale** Hand osteoarthritis (HOA) is a common disease characterized by reduced function, stiffness, and pain. In the most recent American College of Rheumatology guideline for the management of HOA (2020) heating is recommended as a treatment but without scientifically sound evidence of beneficial effects. Further, our local HOA patient partners have via interviews unanimously stated that heat is their preferred treatment for symptom reduction including finger stiffness. Studies assessing the potential benefits of non-pharmacological treatments of HOA are scarce and both ACR, European League against Rheumatism (EULAR) and Osteoarthritis Research Society International (OARSI) recommend exploration of this area. Thus, we find it relevant to investigate if a daily intervention with electrically heated mittens can help reduce pain, improve function and reduce stiffness of the hands in patients with HOA.

**Objectives** The aim of this randomized trial is to investigate the effect of electrically heated mittens after 6 weeks (assessed in week 7) on physical function in patients with HOA compared to sham mittens (inactivated electrical heating).

**Methods** This study is designed as a randomized trial with two parallel groups with change from baseline in physical function of the hand (measured by the AUSCAN questionnaire) as primary endpoint after 6 weeks, with investigators, outcome assessors, and participants being blinded to treatment allocation.

### PICOTS

**Population:** Individuals with HOA.

**Intervention:** Electrically heated mittens worn at least 15 minutes every day, preferably in the morning, for 6 weeks.

**Comparator:** Identically appearing mittens with the electrical heating element being deactivated worn at least 15 minutes every day, preferably in the morning, for 6 weeks.

**Outcome (primary):** Change from baseline to week 7 in the physical function subscale of the Australian/Canadian Osteoarthritis Hand Index (AUSCAN).

**Time:** 6 full weeks.

**Study design:** Randomized trial with two parallel groups.

### Further statistical details

**Randomization:** Computer-generated randomization list was developed based upon permuted random blocks of variable size (2 to 6 in each block). The allocation ratio was 1:1 stratified for the presence of OA of the first carpometacarpal joint (CMC-1).

**Sample size:** A sample size of 200 in total will provide strong statistical power to detect a difference between groups in the primary outcome of 8 AUSCAN-function points (normalized 0-100 scale; equals 81 points on original 0-900 scale). For a two-sample pooled t-test of a normal mean difference with a two-sided significance level of 0.05 ( $P<0.05$ ), assuming a common standard deviation of 19 AUSCAN-function points (normalized 0-100 scale; equals 171 points on original 0-900 scale), a total sample size of 180 HOA patients (i.e. approximately 90 participants per group) has a power of 80.2% to detect a mean difference of 8 AUSCAN-function points (small effect size of 0.42). To account for dropouts, it was decided to include 200 patients in the trial.

**Framework:** This is a superiority trial assessing if electrically heated mittens are superior to sham mittens for improvements in physical function of the hands.

**Statistical interim analyses and stopping guidance:** None.

**Timing of final analysis:** When this statistical analysis plan was finalized and signed, recruitment to the HOT trial had not been completed. We expect recruitment to be completed by the end of March 2023. We will close the database 2 months after the last participant's last visit at the latest. Statistical analyses are expected to be completed after additionally 2 months at the latest.

**Timing of outcome assessment:** (see next section).

**Confidence intervals and P values:** All 95% confidence intervals and P-values will be two-sided.

**Multiplicity:** No explicit adjustments but hierarchical testing of primary and key secondary outcomes.

**Statistical software:** R version 4.0.3 (or newer).

## **2. TABULAR PRESENTATION OF TIMING OF OUTCOME MEASUREMENTS**

---

Week	Baseline	Treatment period						Primary endpoint
	0	1	2	3	4	5	6	7
Window (days from first treatment)	-7 to -1		11 to 17		25 to 31			43 to 50
Clinical examination (TJC & SJC)	X							X
AUSCAN	X		X		X			X
VAS pain/global	X							X
Analgesics	X a	X b	X b	X b	X b	X b	X b	X a
Grip strength	X							X
Mitten use		X b	X b	X b	X b	X b	X b	

AUSCAN, Australian/Canadian Osteoarthritis Hand Index; SJC, swollen joint count; TJC, tender joint count; VAS, visual analog scale.  
a: Interview-based.  
b: Recorded by the participants in a diary.

## **3. ELABORATIONS ON OUTCOMES AND DATA**

---

### **Data management:**

All outcomes: Change from baseline in all outcomes will be calculated as the baseline values minus follow-up values.

AUSCAN: The AUSCAN consists of 3 subscales, AUSCAN function, AUSCAN pain, and AUSCAN stiffness, each with 9, 5, and 1 items, respectively. Each item is scored on a 0-100 mm visual analogue scale (VAS) scale (0, best; 100, worst). Hence, the total scores of each subscale are 0-900 (AUSCAN function), 0-500 (AUSCAN pain), and 0-100 (AUSCAN stiffness).

Tender and Swollen Joint Counts: For the TJC and SJC, 15 joints in each hand are assessed: CMC-1, MCP1 to 5, IP, PIP2 to 5, and DIP2 to 5 in both hands. The scales span from 0 (no tender or swollen joints) to 30 (all joints on both hands are tender or swollen).

VAS pain: In the protocol (page 10) the description of the VAS pain outcome measurement could be read as if the VAS pain assessment was only targeted one hand. In reality, it was targeted the average of both hands and the outcome reflects the average pain intensity across both hands.

Analgesics: Use of analgesics is recorded as use of i) Acetaminophen/paracetamol, ii) NDAIDs, and iii) Other analgesics. The amount is recorded as either 'Almost daily', '2-3 times per week', 'Rarer', or 'Never'. The recording at baseline and primary endpoint is based on an interview with an investigator. In the treatment period (week 1-6) the recording is made by the participant in a diary and recorded once per week. We collapse 'Almost daily' and '2-3 times per week' into a category called 'Analgesic user' and 'Rarer' and 'Never' into the category 'Analgesic non-user'.

### **Data validation:**

All variables used in the analyses, including the derived variables, will be checked for missing values, outliers, and inconsistencies and queried.

### **Data template:**

Based on this SAP, the statistical analyst will develop a tailored data template illustrating the data structure required for the statistical analyses.

#### **4. PROTOCOL DEVIATIONS WITH BEARING ON THIS STATISTICAL ANALYSIS PLAN**

---

The following details in this SAP represent deviations from the trial protocol.

Header in the protocol	Change	Reason
(currently no deviations)		

#### **5. OUTLINE**

---

[figure not shown]
The anticipated (predefined) outline of the manuscript is illustrated below.

Results that only will be presented in the manuscript text include:

- Adherence, defined as number of days that the participants self-report mitten use of at least 15 minutes. The mean number of days for each group will be reported. In case of skewed data medians with interquartile ranges (IQRs) together with difference in medians with 95% confidence intervals will be presented.
- Mitten usage - time. The total amount of self-reported (diary) mitten usage (in minutes) will be reported as descriptive statistics using means and standard deviations for each group, together with a group difference in means with a 95% confidence interval. In case of skewed data medians with IQRs together with difference in medians with 95% confidence intervals will be presented.
- Mitten usage - frequency. The mittens can be used several times per day if participants wish to do so and will be reported as the median with range together with the most frequently reported frequency.
- Mitten intensities. The mittens have 3 heating intensities red (max), yellow (medium), green (min) and the participants record the used intensity in the diary. These will be summarized as proportion of participants who mainly use red, yellow and green intensities during the entire 6 weeks using the number of days with mitten use as denominator for each participant.
- Analgesics use. We will elaborate changes from baseline in the status of analgesic use that may aid in the interpretation of the patient reported pain and function scores.
- Harm outcomes (including adverse events, serious adverse events, and deaths) will be reported as numbers and % in each group. The safety set will be used as the denominator to calculate the percentages. The safety population includes patients who have reported at least one day with at least 15 minutes of mitten usage.
- At the end-of-trial visit, the participants were asked to guess whether the mittens were heated or sham mittens. We will report the degree of blinding success as the agreement between actual allocation and guesses. We will use Cohen's kappa for the analysis as this accounts for correct guesses by chance. A kappa value of 0 indicates successful blinding, and a kappa value of 1 reveals that all the participants can correctly identify a treatment so that the blinding has been completely broken. A positive value implies failure of blinding, whereby most participants correctly guess the treatment allocation above random guessing. A negative value from 0 to -0.20 indicates that participants have been unable to tell the treatment allocations, while a more extreme negative one implied blinding failure in the other direction. We define a kappa value of -0.20 to 0.20 as successful blinding, 0.21 to 0.40 as slightly broken, 0.41 to 0.60 as moderately broken, 0.61 to 1 as severely broken.

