### **Supplementary table 2. Change from baseline in primary and secondary outcomes at week 7 in the per-protocol population**

*[same design as Table 2, but with no p-value column]*

Subgroup analyses using the same model as in the primary analysis, but only including the per-protocol population. The per-protocol population is defined as participants who were randomly assigned to treatment, have a primary outcome data both at baseline and at the primary endpoint assessment, report mitten use of at least 15 minutes on at least 30 days, and who have no major protocol violations (see table in the supplementary file 2).

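### The safety set requires a self-reported 15-minute day, so participants harmed before reaching one drop out of the harm summary

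*SAP*

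**What the plan says.** Section 5 (Outline), in the list of results given only in the manuscript text, covers harms in three sentences. The first sets the content: "Harm outcomes (including adverse events, serious adverse events, and deaths) will be reported as numbers and % in each group". The second sets the base: "The safety set will be used as the denominator to calculate the percentages". The third defines that set: "The safety population includes patients who have reported at least one day with at least 15 minutes of mitten usage".

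The same 15 minutes appears in three other places:

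- PICOTS, as the assigned intervention: "Electrically heated mittens worn at least 15 minutes every day, preferably in the morning, for 6 weeks".
- Section 5, as the adherence measure: "Adherence, defined as number of days that the participants self-report mitten use of at least 15 minutes".
- Supplementary table 2, as part of per-protocol membership: "report mitten use of at least 15 minutes on at least 30 days".

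Mitten use is a diary item. The footnote to the timing table in section 2 reads "Recorded by the participants in a diary". The threshold applies to the day and not to a single session, since section 5 also says "The mittens can be used several times per day if participants wish to do so".

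No other harm population is defined. Item 30 (harms) of the reporting checklist in section 7 only points back to section 5. The supplementary material has no harm table.

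**The concern.** A harm population should follow exposure. This one follows completion, and self-report, of the assigned daily minimum. Either can fail because of the harm itself: someone who finds the heat intolerable in the first minutes and never goes back will not report a qualifying day. That person's event is among those a harm summary of a heating device most needs to show.

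The mechanism is not symmetric. The sham mittens have a deactivated heating element, so exclusion for heat intolerance can happen only in the heated arm. Efficacy, by contrast, is analysed in all randomized participants, subject to available baseline data. The same participant could therefore count towards benefit and not towards harm.

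The numerator is also left open. The SAP ties the safety set to the denominator and does not say whether events outside the set enter the numbers.

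**Working it through.** **Who is left out.** Reading the definition against the other passages:

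| Participant | In the safety set? |
|---|---|
| At least one reported day totalling 15 minutes or more, in one or several sessions, even if they stop afterwards | Yes |
| Harmed in a short first session, later reports one 15-minute day | Yes |
| (a) Used the mittens, was harmed, stopped before any day reached 15 minutes | No |
| (b) Used the mittens but reported no such day, for example because no diary entry exists | No |

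The gap is confined to (a) and (b).

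**Size.** The SAP gives no harm rate and no count of participants below the threshold, so there is no figure of its own to reproduce. The inputs below are assumptions, except that 100 per arm corresponds to the planned 200 at 1:1 allocation:

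- 100 exposed participants in the heated arm;
- 5 harmed participants who qualify for the safety set;
- k harmed participants who never report a 15-minute day (type (a)), with k = 1, 3, 5.

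The three possible rates are:

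- all exposed: (5 + k)/100;
- safety set, outside events left out: 5/(100 − k);
- safety-set denominator, all events counted: (5 + k)/(100 − k).

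| k | All exposed | Safety set, events left out | All events over the restricted denominator |
|---|---|---|---|
| 1 | 6/100 = 6.0% | 5/99 = 5.1% | 6/99 = 6.1% |
| 3 | 8/100 = 8.0% | 5/97 = 5.2% | 8/97 = 8.2% |
| 5 | 10/100 = 10.0% | 5/95 = 5.3% | 10/95 = 10.5% |

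If the sham arm has 5/100 = 5.0% and no exclusions, the heated-minus-sham difference among all exposed is 1, 3 and 5 percentage points. With the events left out it is 0.05, 0.15 and 0.26 points. With k = 0 nothing changes.

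**Sensitivity to the assumptions.** Not everyone excluded need be harmed. If 5 are excluded and 3 of them are harmed, the comparison is 8/100 = 8.0% against 5/95 = 5.3%. If 5 are excluded and none is harmed, as could happen with missing diaries alone, it is 5/100 = 5.0% against 5/95 = 5.3%. So the heated-arm rate is understated when the excluded participants have a higher event rate than those retained, which holds for type (a) by construction and need not hold for type (b). If the same number of harmed participants were excluded from each arm, the difference would be unaffected in this example, but both arms' rates would be too low.

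**The case against.** The strongest counter-argument is that loss of events is inferred. The SAP restricts only the base of the percentages, and nothing expressly restricts the numbers. If events outside the set are counted, none is lost and the percentage is slightly too high: 6.1% instead of 6.0% at k = 1. This stands as a statement of what the text leaves open, but it does not rescue the rule. A percentage on a stated set is ordinarily read as counting events in that set, and on the other reading numerator and denominator refer to different people.

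Second, few participants are likely to be affected, because one qualifying day in six weeks is enough, and the illustration assumes that everyone excluded was harmed and that sham has no exclusions. This stands. The figures show the mechanism over a range and are not an estimate.

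Third, the direction is not certain. Sham participants may also fail to report a qualifying day, and missing diaries have no stated link to arm. This stands in part: the one-sided argument applies to heat intolerance, and the net difference across all reasons for exclusion is unknown.

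Fourth, withdrawal reasons are assigned to Figure 1 (checklist items 24a to 24c), and section 3 has missing values checked and queried, so some cases may surface. Neither is a harm count, and a recovered diary still leaves type (a) outside the set.

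Finally, a wider set may include some people who never wore the mittens, which dilutes the percentages slightly. This is a real but small cost.

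**Conclusion.** The concern holds. The SAP fixes a safety set stricter than exposure, using the adherence threshold and depending on self-report, and it leaves the numerator unstated. Either reading of the numerator gives a percentage that does not describe the exposed participants.

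The actual size cannot be derived from the SAP. Under the assumptions above, with outside events left out, a heated-arm rate of 6.0% to 10.0% would be reported as 5.1% to 5.3%, and a difference from sham of 1 to 5 points would shrink to between about 0.1 and 0.3 points. These figures require that there are harmed participants who never report a 15-minute day and that none of them is in the sham arm. The number is probably small and may be zero.

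Harms are descriptive, and the primary analysis and the testing hierarchy are not affected. The point should be fixed because the rule can hide early heat-related events and is easy to correct.

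**What to change.** In section 5, define the safety set as all randomized participants with any mitten use, whatever its duration. Count participants without diary data as exposed unless they are known never to have used the mittens; using all randomized participants is a simpler alternative. State that all events in these participants are counted in the numerator. Keep the 15-minute threshold for adherence and the per-protocol population only.

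The cost is one or two sentences. Section 5 already plans to summarise diary minutes of use, so any use can be identified wherever entries exist. The harm summary may gain a few participants and show slightly higher event rates. A few participants without diary data may be counted as exposed although they never wore the mittens, which would lower the percentages slightly.

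### The SAP reads any positive kappa as failed blinding, but a guess taken at the end of the trial can give a positive kappa from perceived benefit alone, and the SAP's own bands call values up to 0.20 successful

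*SAP*

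**What the plan says.** The blinding item is in SAP section 5 (Outline), among the results to be reported only in the manuscript text. The only guess it uses is the one at the final visit: "At the end-of-trial visit, the participants were asked to guess whether the mittens were heated or sham mittens". The index is fixed as follows: "We will use Cohen's kappa for the analysis as this accounts for correct guesses by chance".

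The same item then gives two readings of a positive kappa:

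- In a sentence: "A positive value implies failure of blinding, whereby most participants correctly guess the treatment allocation above random guessing".
- In bands: "We define a kappa value of -0.20 to 0.20 as successful blinding, 0.21 to 0.40 as slightly broken", with moderately broken from 0.41 to 0.60 and severely broken from 0.61 to 1.

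The item does not mention an earlier guess, a recorded reason for the guess, or the possibility that participants infer their allocation from how their hands feel.

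**The concern.** By the final visit participants have used the mittens for six weeks and have an opinion on whether they helped. Agreement above chance can then arise in two ways. Participants may have noticed heat or its absence, which is true unblinding. Or they may have guessed from their own improvement, which is a consequence of efficacy. A single end-of-trial kappa mixes the two, yet the sentence assigns every positive value to the first.

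The primary outcome is a questionnaire completed by participants described as blinded, so readers will use the blinding result when deciding how far to believe a positive finding. The reporting rule is predefined. If it stays, the paper could report failed blinding for a small positive kappa that an effective mitten would be expected to produce. The SAP would also support two opposite conclusions for the same value.

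**Working it through.** **Inputs from the SAP** (section 1, Further statistical details)

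- Effect: "to detect a mean difference of 8 AUSCAN-function points (small effect size of 0.42").
- Spread: "assuming a common standard deviation of 19 AUSCAN-function points" on the 0-100 scale.
- Test level: "two-sided significance level of 0.05".
- Size and power: "a total sample size of 180 HOA patients (i.e. approximately 90 participants per group) has a power of 80.2"%.
- Allocation 1:1.

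**Step 1: reproduce the SAP's own figure.** d = 8/19 = 0.421. The noncentrality is 8 / (19 × √(2/90)) = 2.82 on 178 degrees of freedom. The noncentral t gives a power of 80.2%, as stated.

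**Step 2: express kappa in terms of the guesses.** Let a = P(guess heated | heated) and b = P(guess heated | sham). With 1:1 allocation, chance agreement is 0.5 and observed agreement is (a + 1 − b)/2. Hence kappa = [(a + 1 − b)/2 − 0.5]/0.5 = a − b.

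**Step 3: assume perfect blinding and outcome-driven guessing.** This model is not in the SAP. Nobody senses heat, and each participant guesses heated when their own improvement is above the overall midpoint. Then a = Φ(d/2), b = Φ(−d/2) and kappa = 2Φ(d/2) − 1. At d = 0.421, a = 0.583, b = 0.417 and kappa = 0.167.

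**Step 4: sampling spread with 90 per arm.** SE = √(2 × 0.583 × 0.417 / 90) = 0.073. Binomial simulation gives:

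| True difference (0-100 scale) | Expected kappa | P(observed > 0) | P(observed > 0.20) |
|---|---|---|---|
| 4 points | 0.08 | 85% | 5% |
| 6 points | 0.13 | 95% | 14% |
| 8 points (planned) | 0.17 | 99% | 30% |
| 10 points | 0.21 | >99% | 51% |
| 12 points | 0.25 | >99% | 72% |
| 20 points | 0.40 | >99% | >99% |

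With 100 per arm, the planned effect gives 99% and 29%. With no effect and perfect blinding, the observed kappa is still above 0 in about 47% of trials by chance, and above 0.20 in 0.2 to 0.3%.

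**Step 5: vary the guessing model at the planned effect.** With the threshold c SD above the midpoint, kappa = Φ(c + d/2) − Φ(c − d/2). This gives 0.16, 0.15 and 0.10 for c = 0.25, 0.5 and 1. If half the participants guess at random, 0.167/2 = 0.08. Guesses that draw on several outcomes could push kappa up instead.

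**Step 6: where benefit alone crosses the bands.** Expected kappa reaches 0.20 at d = 2Φ⁻¹(0.6) = 0.507, or 0.507 × 19 = 9.6 points. It reaches 0.40 at d = 2Φ⁻¹(0.7) = 1.049, or 19.9 points, which is about 2.5 times the planned effect.

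**Step 7: compare the two readings.** For any kappa above 0 and up to 0.20, the sentence says failure and the bands say success. The value expected from benefit alone at the planned effect, 0.17, lies in that interval.

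**The case against.** The strongest reply is that the bands are the SAP's explicit definition and that they already absorb most of the problem. At the planned effect about 70% of trials would still be labelled successful, even with every guess driven by outcome. A label of slightly broken becomes more likely than not only at about 10 points or more. This stands. A reader might infer that the SAP would declare blinding broken whenever the mittens work as planned. Its bands do not support that; only the separate sentence does.

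A reader might also infer that unblinding through felt warmth could never be recognised from a final guess. That goes too far. Participants who could feel whether the mittens heated would normally still know at week 7, and kappa would be large. Benefit alone reaches 0.40 only at about 20 points, so the ambiguity is confined to modest values.

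The guessing model is also an assumption. It is deterministic, uses one outcome, and cuts at a midpoint that no participant can know. The percentages are therefore illustrations. The direction is not in doubt, because every variant in the working gives a positive expected kappa.

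It is fair, too, that the timing of the question and any recorded reason belong to the protocol and case report form, which are not shown, so their absence here is no fault of the SAP. A guess at week 2 would not be a clean remedy: it also follows the start of treatment and may draw attention to allocation. A verdict based only on guesses attributed to warmth would select on the answer.

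Finally, kappa gates no test and changes no estimate. That limits the severity, but does not make the sentence correct.

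**Conclusion.** The statement that a positive kappa implies failed blinding is wrong as written, for two reasons. First, perceived benefit alone can make an end-of-trial kappa positive. Second, the statement contradicts the SAP's own band for every value above 0 and up to 0.20.

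Under perfect blinding and midpoint guessing at the planned 0.42 SD, expected kappa is about 0.17. The sentence would then report failure in about 99% of trials, and the bands would report slightly broken or worse in about 30%. Looser guessing lowers expected kappa to between 0.08 and 0.16. These sizes rest on an assumed guessing behaviour; the contradiction between sentence and bands rests on the text alone.

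The point is minor. It concerns how one descriptive result is worded, and does not touch the primary analysis, the choice of kappa or the timing of the guess.

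**What to change.** Before unblinding, make two wording changes to the blinding item in SAP section 5:

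1. Delete the sentence that reads a positive kappa as failed blinding, so that only the bands apply.
2. Add that the guess at the final visit also reflects perceived benefit, so a kappa of 0.21 to 0.40 cannot by itself be attributed to failed blinding. Such a value does not show that blinding held either, and the wording should not suggest that it does.

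These changes cost only SAP text and need no new data.

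Optionally, if it is not already collected, ask participants still to attend week 7 for the main reason for their guess (warmth felt or not felt, change in symptoms, other). Report the answers descriptively by arm, without a separate verdict from any subset. This costs one added question. Its limit is that it covers only the remaining participants; the SAP says recruitment was still open when it was signed, so their number depends on when the change is made. No week 2 guess is needed.
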